Comparison of cervical transforaminal epidural corticosteroid injections with lateralized interlaminar epidural corticosteroid injections for treatment of cervicogenic upper extremity radiculopathy

NCT03389620

Document Date: 11/15/2022

Purpose of the Study

Our central hypothesis is that the innovative CT fluoroscopy-guided lateralized interlaminar epidural corticosteroid injection technique will exhibit superior or equivalent efficacy to the traditional transforaminal method for treatment of cervicogenic upper extremity radiculopathy.

SPECIFIC AIM 1: Compare the efficacy of CT fluoroscopy-guided LILESI to that of CT fluoroscopy-guided TFESI in the treatment of patients with cervicogenic upper extremity radiculopathy.

HYPOTHESIS 1: Patient outcomes will be equivalent between the two injection techniques.

1.1 Compare the difference in the primary outcome measure between the two patient groups: numerical pain rating scale (averaged over the past 24 hours) at two months.

1.2 Compare the difference in secondary outcome measures between the two patient groups: numerical pain rating scale (averaged over the past 24 hours) at 2 weeks and 4 months; neck disability index, EQ-5D, and work ability index at 2 weeks, 2 months, and 4 months.

SPECIFIC AIM 2: Compare complication rates between the two injection techniques.

HYPOTHESIS 2: No difference will be seen in complication rates between the two injection techniques.

2.1 Determine the frequency of minor and major adverse events for each group immediately post-procedure and at 2 days after the procedure.

SPECIFIC AIM 3: Determine the technical success rate, defined as the spread of the contrast epidurogram into the neuroforamen, for each of the two injection techniques.

HYPOTHESIS 3.1: The contrast epidurogram will extend into the neuroforamen more frequently with the lateralized interlaminar approach than with the transforaminal approach.

3.1 Determine the frequency of contrast spread into the neuroforamen for each group.

HYPOTHESIS 3.2: Inadvertent intravascular injection will occur more frequently with the transforaminal approach.

3.2 Determine the frequency of inadvertent intravascular contrast injections for each group.

Background & Significance

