Performing an ILESI in which the needle is placed in the far lateral dorsal epidural space adjacent to the facet joint and target neuroforamen, rather than the midline, may result in excellent delivery of medication to the inflamed nerve root. This lateralized interlaminar epidural steroid injection (LILESI) technique has recently been attempted in the lumbar spine where it has been shown to demonstrate equivalent efficacy to TFESI for treatment of lumbar radiculopathy (6, 7). However, this technique has not been studied in the cervical spine and the utility of CT fluoroscopy has not been assessed. Given the excellent precision with needle placement under CT fluoroscopy guidance, it is well suited for performing LILESI in the cervical spine.

The proposed study is innovative because it will be the first to employ CT fluoroscopy-guided LILESI in the treatment of cervicogenic upper extremity radiculopathy. It is also the first study to directly compare treatment efficacy between this new injection type with that of the traditional transforaminal epidural approach. This is significant because demonstration of superior efficacy for LILESI could lead to a paradigm shift in the treatment algorithm for this patient cohort away from TFESI. Additionally, this study could lead to a significant change in practice patterns with a shift toward CT guidance for treatment of cervicogenic radiculopathy, since the LILESI approach cannot be performed under conventional fluoroscopy.

Design & Procedures

Cervical Epidural Corticosteroid Injections

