At the time of the patient's phone call to our office for the purpose of scheduling their procedure, patients referred to our team for treatment of cervicogenic upper extremity radiculopathy will be asked by our staff if they would be potentially interested in discussing a clinical trial. Those that are not interested will not be further contacted about the study. Those that are willing to discuss further will then be referred to our clinical research coordinator (CRC). The CRC will contact the patient (at least one day) prior to their arrival to our clinic for the injection (see attached phone script). At the time of this phone call, potential subjects will be given an overview of the study and then asked if they are interested in participating. If they are interested in participating, the MD performing the injection (either [name] or [name]) will be notified on the day of the patient's procedure. At the time of the patient's visit, the MD will discuss with them their pain pattern, imaging findings, and diagnosis, and will explain how CT guided cervical epidural corticosteroid injections are performed as well as a discussion of the risks and benefits of these procedures. This will all be done prior to any discussion of the clinical trial. At this point, if a potential subject meets the inclusion and exclusion criteria, the CRC will be notified and written informed consent will be obtained from the patient by the CRC on the date of the patient's procedure using the standard IRB-approved consent processes.

Study Interventions

The main intervention in this study is randomization into either of the two treatments arms (described in detail above). This should have negligible effect upon the patients as there is no known difference in risk between the two procedures and the difference in the efficacy between the two procedures is unknown (and the purpose of this study).

Risk/Benefit Assessment

Because both injection types investigated in this study (LILESI and TFESI) are currently used in our institution as part of standard-of-care for treatment of cervical radiculopathy, there is no excess medical risk to subjects as a result of the study randomization.

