Based on a power of 0.8 (alpha 0.05) to detect superiority of the LILESI group, assuming positive response rates of 45% for the TFESI group and 70% for the LILESI group, we would need a total of 116 patients (57.5 patients in each arm). This sample size would also give us a power of 0.99 to detect non-inferiority (i.e. equivalence between TFESI and LILESI) (non-inferiority margin 0.1).

Patient Outcome Analysis

A reduction of 2 points from baseline on the NRS will be considered a positive response (clinically meaningful or moderate improvement per IMMPACT consensus statement) (15). Primary Endpoint (average NRS over the past 24 hours at 2 months time point): We will apply a difference test and a non-superiority test for binomial proportion to test the primary endpoint. Secondary Endpoints: The secondary endpoints will be analyzed using a test for difference in binomial proportions or a t-test for binomial or semi-continuous variables, respectively.

Interim Data Analysis

An interim analysis will be performed of the first 58 patients by the biostatistician (co-investigator). All study participants, assessors, and other personnel (including other co-investigators) will remain blinded. Safety and efficacy will be evaluated using an O'Brien–Fleming stopping rule of $p < 0.001$ for the interim analysis in order to evaluate for early evidence of treatment efficacy (26).

Crossover, Withdrawal, or Missing Data

We will employ an intention-to-treat (ITT) analysis for this trial (27). Patients that crossover between study arms, withdraw from the study, or for whom there is missing data will all be handled in the same manner. A conservative approach will be taken and we will assume that the patient will receive no further benefit from the study injection. As such, the most recent available outcomes data will be extrapolated to all later time points for which no data are available.

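### The 0.99 non-inferiority power assumes LILESI is 25 points better; at equal response rates it is about 0.2 to 0.3, and the analysis text misnames the test

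*Combined protocol and SAP*

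**What the plan says.** Sample Size Determination sets the trial size on superiority: "Based on a power of 0.8 (alpha 0.05) to detect superiority of the LILESI group". It gives the rates behind this in the words "assuming positive response rates of 45% for the TFESI group and 70% for the LILESI group", and arrives at 116 patients in total. The next sentence says that this number also gives a "power of 0.99 to detect non-inferiority (i.e. equivalence between TFESI and LILESI) (non-inferiority margin 0.1"). No other true rates are offered for that second figure.

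Patient Outcome Analysis defines a responder by a 2-point reduction in NRS from baseline. It then gives the whole of the primary analysis in one sentence: "We will apply a difference test and a non-superiority test for binomial proportion to test the primary endpoint". Non-superiority is not defined, and no non-inferiority test is named in the analysis text. None of the tests is said to be one-sided or two-sided, and the scale of the 0.1 margin is not given.

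Purpose of the Study puts the central hypothesis as LILESI that "will exhibit superior or equivalent efficacy to the traditional transforaminal method". Hypothesis 1 is narrower: "Patient outcomes will be equivalent between the two injection techniques". Background & Significance says of the lumbar version of the technique that "it has been shown to demonstrate equivalent efficacy to TFESI for treatment of lumbar radiculopathy". Study Interventions says that "the difference in the efficacy between the two procedures is unknown".

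**The concern.** The central hypothesis has two branches, superior or equivalent. The first has a test and a sample size that fit each other. The second is where the difficulty lies.

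The plan attaches a power of 0.99 to the second branch and describes it as power for equivalence. A reader will take this to mean that, if the techniques perform alike, the trial is almost certain to show it. That would hold only if the 0.99 had been worked out at equal or nearly equal rates. If it was worked out at 45% versus 70%, it describes a trial in which LILESI is clearly better, which is not the situation in which the fallback claim is needed.

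The analysis sentence adds to this. Read literally, a non-superiority test addresses a different hypothesis from the one that was powered. Even with the word corrected, the level and the interval method stay open, and these can decide a close result after the data are seen.

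**Working it through.** **Inputs.** From Sample Size Determination: alpha 0.05; rates pT = 0.45 and pL = 0.70; total 116, taken as 58 per arm; margin 0.1. Sidedness and margin scale are not stated, so both levels are shown and the scale is checked. All power figures use the normal approximation with unpooled variance and make no allowance for the interim look.

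**1. Reproduce the sample size.** n per arm = (1.960 + 0.842)² × [0.45×0.55 + 0.70×0.30] / 0.25² = 57.45, so 58 per arm and 116 in total. This matches the plan and implies a two-sided 0.05 superiority test. The power at 58 per arm is Φ(0.25/0.0888 − 1.960) = 0.804.

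**2. Reproduce the 0.99.** Non-inferiority power = Φ((pL − pT + 0.10)/SE − z), with SE = √{[pT(1−pT) + pL(1−pL)]/58}. At 45% versus 70%, SE = 0.0888:
- z = 1.645 (one-sided 0.05): Φ(0.35/0.0888 − 1.645) = 0.989
- z = 1.960 (one-sided 0.025): 0.976

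So the stated figure is reproduced with an absolute margin, best at one-sided 0.05. A ratio margin of 0.90 gives Φ((ln(0.70/0.45) − ln 0.90)/0.1687 − z) = 0.945 (0.900 at one-sided 0.025), which does not match. The absolute scale can therefore be inferred.

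**3. Change only the true LILESI rate** (TFESI 45%, absolute margin 0.10):

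| True LILESI rate | One-sided 0.05 | One-sided 0.025 |
|---|---|---|
| 70% | 0.989 | 0.976 |
| 65% | 0.953 | 0.912 |
| 60% | 0.860 | 0.778 |
| 55% | 0.699 | 0.581 |
| 50% | 0.490 | 0.367 |
| 45% (equal) | 0.287 | 0.190 |

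The last row is Φ(0.10/0.0924 − z). With both rates at 70%, SE = 0.0851 and the power is 0.319 (0.216). Exact binomial enumeration of the same Wald rule gives 0.289 (0.201) at 45%/45% and 0.324 (0.223) at 70%/70%. Power reaches 0.80 only when the true LILESI rate is about 58% (61%), that is, 13 (16) points better.

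**4. Two-sided equivalence.** At equal 45% rates the half-width of the 90% interval is 1.645 × √(2×0.45×0.55/58) = 0.152. This exceeds 0.10, so the interval cannot fit inside ±0.10 at rates near these. Exact power is below 0.000001 at common rates of 45%, 57.5% and 70%.

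**5. Do the unstated choices matter?** Take 26/58 TFESI responders.
- LILESI 29/58: the 90% lower limit is −0.1006 by Wald (fails) and −0.0988 by Newcombe (passes).
- LILESI 30/58: the Wald lower limit is −0.083 at 90% (passes) and −0.112 at 95% (fails).

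**The case against.** Much can be said for the plan. The word non-superiority is very likely a slip: alpha, margin, direction and the term non-inferiority all stand one paragraph above it, and most readers would reconstruct the intended test. The margin scale can be recovered, as step 2 shows. The 0.99 is not a miscalculation, and its assumption is not hidden, since it follows directly on the sentence giving 45% and 70%. Quoting non-inferiority power under the design alternative is coherent with a hypothesis of superior or equivalent. The plan does not propose a two-sided equivalence test; it uses the word as a gloss on non-inferiority. Support for exactly equal rates is also limited: the lumbar result comes from cited work, the plan calls the cervical difference unknown, and equivalent in Hypothesis 1 need not mean identical.

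All of this stands, and it removes the stronger readings that a reader might infer. The documents do not show an arithmetic error in the 0.99, a deliberately wrong test, or a sample size that fails its stated purpose. Nor is equal-rates power below one third at every response rate: at one-sided 0.05 it passes that level once the common rate exceeds about 73% (0.344 at 75%). The statement is limited to 45% to 70%.

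What the objection does not answer is the gloss itself. A power that needs a 25-point advantage is offered as power for equivalence, beside a hypothesis that outcomes will be equivalent. Sidedness also remains unstated.

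**Conclusion.** The point holds and should be fixed. The 0.99 is power for non-inferiority when LILESI is truly 25 points better than a 45% TFESI rate. It is not the power to support Hypothesis 1. At equal true rates between 45% and 70%, with 58 per arm and an absolute 0.10 margin, the power is about 0.29 to 0.32 at one-sided 0.05, or 0.19 to 0.22 at one-sided 0.025. Two-sided equivalence within ±0.10 is out of reach at this size.

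The misnamed test is secondary and probably editorial, but the sentence containing it is the only statement of the primary analysis. Once the word is corrected, the level and interval method still have to be fixed in advance.

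A reader might conclude that the trial is too small. The documents do not support that: 116 was derived for superiority, it reproduces, and the difference test serves that claim. Only the fallback claim is affected. The results rest on the inferred absolute scale, on 58 analysed patients per arm, and on the normal approximation, which the exact enumeration supports.

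**What to change.** 1. In Patient Outcome Analysis, replace the non-superiority wording with: a non-inferiority test of LILESI versus TFESI on the absolute difference in 2-month response proportions, met if the lower limit of the confidence interval for LILESI minus TFESI exceeds −0.10. Name the interval method in advance (for example Newcombe) and the level. A two-sided 90% interval (one-sided 0.05) matches the stated 0.99. If the sponsor chooses the 95% interval (one-sided 0.025), restate the power as about 0.98. The choice of level is the sponsor's.
2. Beside the 0.99, state that it assumes 45% versus 70%, and give the equal-rates power: about 0.29 at a common rate of 45%, or 0.19 at one-sided 0.025.
3. Delete the gloss that equates non-inferiority with equivalence. State that a met test supports non-inferior and not two-sided equivalent, which 116 patients cannot show within ±0.10 at response rates of 45% to 70%.

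The cost is a few sentences and a less favourable power statement. N stays at 116, and no data are added.

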We will employ a single-center, parallel, randomized, prospective design. Enrolled patients will be assigned to one of two treatment arms using a block randomization scheme: transforaminal cervical epidural corticosteroid injection or lateralized interlaminar cervical epidural corticosteroid injection. Baseline data will be collected including duration, location, and character of pain; numerical pain scale (NRS); neck disability index (NDI); EQ-5D; and work ability index (WAI) (see Outcome Measures below). All procedures will be performed under CT fluoroscopy on the same scanner. The cervical level of injection for patients in both treatment arms will be at the discretion of the treating physician and will be based on symptoms (e.g., dermatomal distribution of pain) and imaging findings. All injections will be performed by a board certified radiologist with a certificate of added qualification in neuroradiology and at least five years of experience in CT fluoroscopy-guided spine injections. Patients and outcome assessors (clinical research coordinator) will remain blinded to the treatment assignment throughout

the study. In order to maintain blinding of patients and appropriate study personnel throughout the trial, billing / charges will be held until the patient reaches the final endpoint of the study or withdraws from the study. The research coordinator will be the study personnel who records the billing at this point, however, all outcome assessments will have been completed already ensuring that they remain unbiased. The treating physicians are unable to be blinded, as they will be aware of the type of patching material used. The effectiveness of patient blinding will be assessed using the Bang Blinding Index prior to discharge on the day of the procedure (8). Patients will become unblinded to their treatment assignment at the end of their participation in the study (either at the conclusion of the study after the final outcome measure time point (i.e. 4 months) or if they elect to withdraw from the study at any time).

Transforaminal Cervical Epidural Corticosteroid Injections (TFESI)

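### The unadjusted primary comparison uses neither baseline NRS nor operator; prespecifying adjustment for both is a small gain in precision at almost no cost

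*Combined protocol and SAP*

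**What the plan says.** All references are to the combined protocol and SAP.

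- **Primary test.** Patient Outcome Analysis: "We will apply a difference test and a non-superiority test for binomial proportion to test the primary endpoint". No stratum, covariate or model is named for this test or for the secondary endpoints. I read the second test as the non-inferiority test with margin 0.1 in Sample Size Determination; the two terms need to be made the same.
- **Responder definition.** "A reduction of 2 points from baseline on the NRS will be considered a positive response". Baseline NRS is therefore part of the outcome. Patient Outcome Measures has it collected before the procedure, and Selection of Subjects requires a value above 4 for entry.
- **Operators.** Subject Recruitment and Compensation refers to "the MD performing the injection" and says that this is one of two named physicians. That physician sees the patient before the coordinator takes consent, so the operator can be known before allocation.
- **Randomization.** Design & Procedures: "Enrolled patients will be assigned to one of two treatment arms using a block randomization scheme". No stratification factor is stated.
- **Operator qualification.** Same section: "All injections will be performed by a board certified radiologist with a certificate of added qualification in neuroradiology", with at least five years of experience in these injections. Risk/Benefit Assessment also describes the operators as highly experienced.
- **Sample size.** The calculation targets 80% power at alpha 0.05 for LILESI being superior. Its inputs are given as "assuming positive response rates of 45% for the TFESI group and 70% for the LILESI group", and it arrives at 116 in total.

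The documents give no operator-specific response rate and do not say how operator enters the analysis.

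**The concern.** Two baseline variables could plausibly explain part of the variation in response, and the primary test uses neither.

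Baseline NRS is built into the response: how far a patient's score can fall depends on where it starts. Operator is plausible because the trial compares two manual needle techniques and leaves the level of injection to the treating physician. The experience requirement covers CT-guided spine injections in general, while the Background says that the lateralized technique has not been studied in the cervical spine.

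At stake is precision in a trial with no slack: the sample size carries no dropout allowance and only just meets its power target. An adjusted analysis also takes account of whatever imbalance in these factors has actually arisen. Adjustment is credible only if it is fixed before the data are seen.

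**Working it through.** **1. Reproduce the plan's figures.** Inputs from Sample Size Determination: 45% and 70%, power 0.80, alpha 0.05 (sidedness not stated; two-sided fits).

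n per arm = (1.95996 + 0.84162)² × (0.45×0.55 + 0.70×0.30) / 0.25² = 7.8489 × 0.4575 / 0.0625 = 57.45.

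This matches the stated 57.5 per arm and 116 in total, using the unpooled variance. At 58 per arm the pooled z test has power 0.785. The 0.78 below is that pooled figure; it is not a shortfall caused by operators.

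Standard error of the difference: √(0.4575/58) = 0.0888, or 8.9 points. Non-inferiority power at 45% v 70%: (0.25 + 0.10)/0.0888 − 1.645 = 2.30, giving 0.989, the stated 0.99 (one-sided 0.05).

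**2. How much variance operator could remove.** With a 50:50 share and a response gap g between operators, the removable variance is g²/4. The average binomial variance is 0.4575/2 = 0.229.

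- g = 10 points: 0.0025/0.229 = 1.1%, about 1 of 116 patients
- g = 20 points: 0.0100/0.229 = 4.4%, about 5 patients
- g = 30 points: 0.0225/0.229 = 9.8%, about 11 patients

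**3. Superiority power by simulation.** 58 per arm, 45% v 70%, allocation not stratified by operator; crude pooled z test against a Cochran-Mantel-Haenszel test by operator. 200,000 trials per row, or 60,000 where marked *. The gaps are assumptions.

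| Operator gap | Crude (50:50) | Stratified (50:50) | Stratified (70:30) |
|---|---|---|---|
| 0 | 0.784 | 0.783 | 0.781 |
| 10 points | 0.782 | 0.785 | 0.787 |
| 15 points* | 0.783 | 0.793 | 0.791 |
| 20 points | 0.782 | 0.800 | 0.798 |
| 25 points* | 0.783 | 0.810 | 0.807 |
| 30 points | 0.785 | 0.825 | 0.817 |

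The crude column is flat. In the 200,000-trial runs the crude type I error was 4.8% to 4.9% and the mean estimate 0.250, so there is no bias and no invalid test.

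**4. Chance imbalance.** The between-arm difference in one operator's patients averages about 4, with a 95th percentile of 10. A difference of 10 is 10/58 = 17% of an arm and shifts the crude estimate by 0.17 × g: 1.7, 3.4 or 5.2 points for gaps of 10, 20 or 30. The crude standard error of 8.9 points already contains this.

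**5. Baseline NRS.** Assumed: baseline 5 to 10 with SD 1.5, 2-month SD 2.5, correlation r between them; 15,000 trials; response rates held at 45% and 70%. Crude power was 0.776 to 0.783. Logistic adjustment gave 0.779 (r = 0.5), 0.797 (0.4), 0.802 (0.3) and 0.818 (0.2).

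The direction is as expected. The covariance of improvement with baseline is 1.5² − r×1.5×2.5, which is 1.5 at r = 0.2 but only 0.375 at r = 0.5. The more closely the two scores track, the less baseline says about the change.

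**6. Non-inferiority.** Margin 0.1, one-sided 0.025 (assumed), crude against an operator-stratified Mantel-Haenszel risk difference.

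- True rates 45% and 70%: crude 97.3%; stratified 97.2% (gap 10) and 97.6% (gap 20).
- Equal rates of 55% (assumed): 20.0% v 19.6% (gap 10), 20.0% v 20.1% (gap 20), 20.2% v 21.1% (gap 30).

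**7. What a per-operator comparison can show.** With about 29 patients per arm per operator, the 95% half-width is 1.96 × √(0.4575/29) = 25 points. For the contrast between operators it is 25 × √2 = 35 points.

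**The case against.** The best case against acting is that the benefit depends on an operator gap for which the documents offer no evidence. What they do say points towards similar operators: the same qualifications, the same scanner, the same drug and volume. At gaps of 0 to 10 points stratification gains nothing that matters. This stands, and it is why the gain must be called small and conditional.

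Four stronger readings are tempting, and the documents do not support them.

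- *Operator differences bias the crude test or erode its power.* They do neither: the binomial variance already includes the spread between operators.
- *Chance imbalance between operators is an error on top of the stated uncertainty.* It is inside the crude standard error.
- *Stratifying protects against a result driven by one operator.* That would be an operator-by-technique interaction. A stratified main effect averages over it, and the per-operator intervals are too wide to detect or exclude it.
- *The randomization is shown to be unbalanced by operator.* The plan only states no stratification factor.

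The choice of estimator also matters. A Mantel-Haenszel risk difference with the usual Sato variance gave a two-sided type I error of 5.3% to 5.5%, against 5.0% to 5.1% for the crude unpooled test. That excess is not trivial beside gains of this size, so the plan should name one estimator and one variance method.

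What the objection does not answer is the cost side. With no operator effect, stratifying loses about 0.1 power point (0.784 v 0.783), and baseline NRS is already collected.

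**Conclusion.** The point holds as a free improvement with a small gain. The planned test is sound but leaves available precision unused. For superiority, operator adjustment is worth about nothing for a gap of 0 to 10 points, about 2 power points at 20 and about 4 at 30. Baseline NRS is worth about 0 to 4 points for assumed correlations of 0.5 down to 0.2. The two gains were simulated separately and should not simply be added. For non-inferiority, the operator gain is about 0 to 1 point; the low power of that test when the rates are equal is a separate matter that adjustment does not cure.

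The results rest on the plan's 45% and 70%, 58 per arm with no losses, an operator effect equal in both arms, and assumed operator gaps, baseline distribution and correlations. A reader should not infer that the trial's primary result would be wrong without this change.

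**What to change.** Change the primary analysis text to name one estimator for both the difference and the non-inferiority test: a logistic model for response with arm, baseline NRS (linear) and operator, standardized over all randomized patients to a LILESI minus TFESI risk difference with a confidence interval.

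- State the variance method, and check its type I error by simulation at 58 per arm before unblinding.
- State the sidedness and level of each test, and whether the interim look at 58 patients uses the same model.
- Keep the crude comparison of proportions as a sensitivity analysis.
- Record operator for every patient as a study variable, and use the operator identified before allocation if there is a change on the day.
- Report the difference for each operator descriptively only, noting that about 29 patients per arm per operator cannot establish or exclude an operator-by-technique interaction.
- Leave the randomization unchanged.

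The cost is SAP wording, a short program and one recorded field. No extra patients, visits or questionnaires are needed. The documents do not say that operator is captured in the study data, but with two physicians who each meet the patient on the procedure day, it should be simple to record.

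### Hypothesis 1 predicts equivalence, but the trial is sized for superiority and labels one-sided non-inferiority as equivalence; neither primary test can show equivalence, and no rule links results to conclusions

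*Combined protocol and SAP*

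**What the plan says.** Three statements of purpose bear on the same comparison.

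- Purpose of the Study, central hypothesis: LILESI "will exhibit superior or equivalent efficacy to the traditional transforaminal method".
- Specific Aim 1: "HYPOTHESIS 1: Patient outcomes will be equivalent between the two injection techniques".
- Sample Size Determination: "Based on a power of 0.8 (alpha 0.05) to detect superiority of the LILESI group". The response rates taken for this are 45% with TFESI and 70% with LILESI, and the result is 116 patients. The same paragraph says that this number also gives a "power of 0.99 to detect non-inferiority (i.e. equivalence between TFESI and LILESI) (non-inferiority margin 0.1").

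Patient Outcome Analysis defines a responder as a patient whose NRS falls by 2 points from baseline, and then says of the 2-month primary endpoint: "We will apply a difference test and a non-superiority test for binomial proportion to test the primary endpoint". It gives no order, sidedness or alpha for the two tests, does not attach the 0.1 margin to the second one, and does not say what is concluded from each pattern of results. No other section supplies these. The interim rule (p < 0.001) does not name the test it applies to.

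**The concern.** Equivalence means that the difference is small in both directions. A difference test cannot show that: a significant result shows the arms differ, and a non-significant one shows only that a difference was not detected. A one-sided margin test cannot show it either, because it bounds the difference on one side only and is passed most easily when LILESI is much better. So the hypothesis named under Specific Aim 1 has no test that could support it, and the label in the sample-size section hides this.

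At stake is the wording of the primary conclusion. A trial in which LILESI is clearly better would meet the plan's criterion for equivalence. A trial in which nothing is shown has no conclusion assigned to it, so the wording would be settled after the data are seen.

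**Working it through.** **Inputs.** From Sample Size Determination: rates 45% (TFESI) and 70% (LILESI), power 0.80, alpha 0.05, margin 0.1, 116 patients, taken as 58 per arm. Assumptions, because the plan does not state them: the second test is non-inferiority of LILESI with margin 0.1; its one-sided alpha is 0.05 or 0.025 (both shown); the difference test is two-sided at 0.05.

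**1. The plan's sample size.** Unpooled normal approximation, two-sided 0.05:

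n per arm = (0.45×0.55 + 0.70×0.30) × (1.960 + 0.842)² / 0.25² = 57.45, so 58 per arm and 116 in total. The stated figure reproduces.

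**2. The plan's non-inferiority power.** At 45% and 70%:

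SE = √[(0.2475 + 0.2100)/58] = 0.0888; (0.25 + 0.10)/0.0888 = 3.94.

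- One-sided 0.05: Φ(3.94 − 1.645) = 0.989.
- One-sided 0.025: Φ(3.94 − 1.960) = 0.976.

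The stated 0.99 reproduces, but at rates where LILESI is 25 points better. Exact binomial enumeration gives 0.988 and 0.973. So the criterion that the plan calls equivalence is met in about 0.97 to 0.99 of trials when the arms are far apart.

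**3. Power for two-sided equivalence at margin 0.1.** Two one-sided tests at 0.05 succeed only if the 90% confidence interval lies wholly within ±0.1. With equal true rates p, its half-width is 1.645 × √[2p(1−p)/58]:

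- p = 0.45: 1.645 × 0.0924 = 0.152.
- p = 0.70: 1.645 × 0.0851 = 0.140.

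Both exceed 0.1, so even an observed difference of zero would fail. Enumeration gives power of zero to three decimals.

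**4. Non-inferiority power if the arms are truly equal (assumption: 45%, 57.5% or 70% in both).** Φ(0.1/SE − z):

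| True rate in both arms | One-sided 0.05 | One-sided 0.025 |
|---|---|---|
| 45% | 0.287 | 0.190 |
| 57.5% | 0.289 | 0.192 |
| 70% | 0.319 | 0.216 |

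Enumeration gives 0.29 to 0.32 and 0.20 to 0.22.

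**5. How the two tests relate.** Over all possible outcomes with 58 per arm (pooled z for the difference, unpooled z for the margin), no result significant for LILESI fails the margin test and none significant for TFESI passes it, at either alpha. The tests are nested.

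**6. Two example data sets (TFESI, then LILESI).**

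- 26/58 and 41/58: difference 0.259, p = 0.005, 95% CI 0.085 to 0.432. The lower limit is above −0.1, so the plan's equivalence label applies to a result that shows superiority.
- 26/58 and 26/58: difference 0, p = 1.0, 95% CI −0.181 to 0.181. Non-inferiority is not shown, and the plan assigns no conclusion.

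**The case against.** The strongest reply is that this is a familiar pairing of superiority and non-inferiority, loosely worded. The central hypothesis allows either outcome, the sample size is driven by superiority, and the plan says in terms that it uses equivalence to mean non-inferiority. On that reading a superior LILESI is also non-inferior, and nothing conflicts. Much of this stands: the nesting in step 5 confirms it, and testing the pair in sequence needs no split of alpha. It does not rescue Hypothesis 1, which predicts equivalent outcomes without qualification, and a sequence that is not written down does not bind the analysis.

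Stronger readings are tempting but not supported.

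- *The two tests contradict each other, so the same data confirm and refute Hypothesis 1.* As tests they do not conflict. That both succeed in about 78% of trials at 45% and 70% is simply the power of the difference test (0.784). The clash is between a two-sided hypothesis and a one-sided label.
- *Equal arms usually give no positive result, so the decision rule fails.* Neither test succeeds in about 65% to 69% of such trials (75% to 78% at one-sided 0.025), but that reflects low margin-test power, which a decision rule does not change.
- *The plan will report a non-significant difference as equivalence.* If LILESI were 10 points worse, the difference would be non-significant in about 80% of trials. No section, however, prescribes that reading for the primary endpoint.

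The second test is called non-superiority. Taken literally with margin 0.1, it would be met in about 0.001 of trials or fewer at 45% and 70%, and never together with a significant LILESI advantage. The figures above therefore depend on reading it as non-inferiority, as the sample-size section suggests. On the literal reading it is still one-sided and still cannot show equivalence.

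**Conclusion.** The concern holds as a mismatch between hypothesis, label and tests. The plan predicts equivalence, is sized for superiority, and would attach the word equivalence to a one-sided result that is met in about 0.97 to 0.99 of trials when LILESI is truly 25 points better. At margin 0.1 with 58 per arm, genuine two-sided equivalence is out of reach. The sample-size arithmetic is sound, and type I error is not inflated by running both tests. The stated 0.99 applies only if LILESI is truly superior by the planned amount. These conclusions assume 58 evaluable patients per arm, a non-inferiority reading of the second test, and a one-sided alpha of 0.05 or 0.025. The sponsor should correct this, because it determines what the primary result may be said to show.

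**What to change.** 1. Reword Hypothesis 1 for the primary endpoint, and the equivalence gloss in Sample Size Determination, to: LILESI is non-inferior to TFESI (margin 0.1). Name the second test accordingly.
2. State one fixed sequence, read from a single two-sided 95% confidence interval for the 2-month responder difference (LILESI minus TFESI), so that non-inferiority is tested at one-sided 0.025:
   - lower limit above −0.1: non-inferior;
   - lower limit above 0: superior;
   - otherwise: non-inferiority not shown.
3. State that a non-significant difference will not be reported as equivalence.
4. Say which of the two comparisons the interim rule applies to.

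This takes a few sentences, with no added patients, data or alpha. It has two downsides, which should be stated openly. A non-significant difference can no longer be presented as confirming Hypothesis 1. And if the true rates are equal at 45% to 70%, the chance of showing non-inferiority is only about 0.20 to 0.22 (0.29 to 0.32 at one-sided 0.05). For scale, 80% power at one-sided 0.025 would need 2p(1−p) × (1.960 + 0.842)² / 0.1² per arm: about 389 at 45% and 330 at 70%. The rewording does not require that number, but the 0.99 should be reported together with the rates it assumes.
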